Clearly, therefore, a prospectively randomized study needs to be set up to determine whether GLP-1RAs reduce the progression of albuminuria or reverse albuminuria. If indeed, this is shown to be true, we shall have an anti-diabetic drug class which for the first time will have an effect on the development of microangiopathy in addition to its role as an anti-hyperglycemic agent. In this proposal, we intend to investigate the hypothesis that treatment of with weekly exenatide reduces the rate of progression of albuminuria in patients with type 2 diabetes.

Preliminary data:

1- Effect of GLP-1 RA on evolution of albuminuria in type 2 diabetes: A retrospective study.

Among 466 patients with type 2 diabetes, 70.6 % (n=329) had normoalbuminuria, 24 % (n=112) had microalbuminuria and 5.1 % (n=24) had macroalbuminuria. Over a mean 3 year follow up, there was a reduction in UACR in the entire group by 21.1 ± 328 mg/g from a mean of 85.8 ± 374 mg/g to 65.1 ± 225 mg/g. In group A, UACR fell by 37 ± 193 mg/g (from 87 ± 250 mg/g to 49.8 ± 147 mg/g, $p < 0.0001$), while in group B, UACR increased by 6 ± 454 mg/g (from 81.1 ± 500 mg/g to 87 ± 302 mg/g, $p < 0.05$) ($p < 0.001$ between groups).

Since there was a significant difference in the reduction of HbA1c between groups A and B, we carried out a secondary analysis on UACR differences to adjust for the fall in HbA1c. UACR changes from baselines were first log transformed and difference between groups were tested with ANCOVA with changes in HbA1c used as a covariate. HbA1c adjusted log change in UACR in group A was -0.09 ± 0.49 and in group B was 0.08 ± 0.056 ($p = 0.007$, ANCOVA).

In the entire cohort (n=466), those with baseline normoalbuminuria (n=329), 88.7 % (n=292) remained normal, 10% (n=33) developed microalbuminuria and 1.2% (n=4) developed macroalbuminuria. Among those with baseline microalbuminuria (n = 112), 47.3% (n = 53) regressed to normal, 47.3 % (n =53) remained microalbuminuric, while 5.3 % (n=6) progressed to macroalbuminuria. Among those with baseline macroalbuminuria (n=24), 4% regressed to normal, and 50% regressed to microalbuminuria while 46 % remained macroalbuminuric.

The GLP-1RA users (group A; n =275) were followed up for a mean of 2.3 years.

[figure not shown]

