- (a) Among those who had normoalbuminuria at baseline (n=183), 171 (93.4%) remained normal, 10 developed microalbuminuria (5.4%) and 2 developed macroalbuminuria (1%) as depicted in Figure 1. The mean UACR changed from 9.4 ± 7.1 mg/g to 18.1 ± 17.2 mg/g. The mean creatinine concentration changed from 0.98 ± 0.38 mg/dl to 1 ± 0.34 mg/dl. The eGFR decreased by 5.1 ± 18.4 ml/min from 95.7 ± 31.3 ml/min to 90.7 ± 30.2 ml/min. The mean HbA1c decreased by 0.7 ± 1.7 % from 7.9 ± 1.7 % to 7.2 ± 1.4 %.
- (b) Amongst 76 patients who had baseline microalbuminuria, 44 patients (57.8%) normalized while 32 (42.1%) remained microalbuminuric during follow up. No patient developed macroalbuminuria. The mean UACR fell by 57.7 ± 64.5 mg/g from 103.5 ± 68.8 mg/g to 45.8 ± 48.7 mg/g, a decrease of 42 ± 74 %. The mean creatinine changed from 1.04 ± 0.34 to 1.15 ± 0.42 mg/dl. The mean eGFR decreased by 8.6 ± 18 from 90.2 ± 36.9 ml/min (Table 2). Even in those who remained microalbuminuric, 22 had a reduction in UACR of 71.1 ± 54 mg/g from 155.4 ± 74 mg/g to 84.3 ± 55 mg/g. The mean HbA1c decreased by 0.8 ± 2.2 % from 8.4 ± 2 % to 7.6 ± 2 % in this group. The 10 patients who had no reduction in UACR had a significant increase in HbA1c from 9.2 ± 1.2 % to 9.7 ± 2.7 %.
- (c) Among the 15 patients who had macroalbuminuria at baseline, 1 normalized (6.6%), 8 became microalbuminuric (53.3%), and 6 remained macroalbuminuric (40%). The mean UACR fell by 500 ± 606 mg/g from 936 ± 579 mg/g to 436 ± 398 mg/g, a decrease of 40 ± 57 %. The mean creatinine increased from 1.37 ± 0.6 mg/dl to 1.47 ± 0.6 mg/dl. The eGFR decreased from 76.5 ± 36.5 ml/min to 70.1 ± 34.6 ml/min. The mean HbA1c decreased by 1 ± 1.2 % from 8.4 ± 1.8 % to 7.4 ± 1.6 %.

The GLP-1RA non-users (group B; n=191), were followed up for a mean period of 3.6 years.

- a) 146 patients had normo-albuminuria at baseline. Of these, 121 (82.8%) remained normal, 23 (15.7%) developed microalbuminuria and 2 developed macroalbuminuria (1.3%). The mean UACR increased by 20.6 ± 81 mg/g from 8.1 ± 6.9 mg/g to 28.7 ± 82.4 mg/g. The mean creatinine remained stable from 1 ± 0.36 mg/dl to 1.04 ± 0.39 mg/dl. The eGFR decreased from 89.1 ± 27.9 ml/min to 87.4 ± 29.5 ml/min. The mean HbA1c decreased by 0.4 ± 1.8 % from 7.5 ± 1.7 % to 7.1 ± 1.4 %.

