- b) 36 patients had microalbuminuria at baseline. Of these, 9 normalized (25%), 21 remained microalbuminuric (58.3%) and 6 developed macroalbuminuria (16.6%). The mean UACR increased by 60 ± 201 mg/g from 85 ± 48 mg/g to 145 ± 199 mg/g, an increase of 105 ± 311 %. The mean creatinine changed from 1.06 ± 0.39 mg/dl to 1.2 ± 0.46 mg/dl. The eGFR decreased by 12.1 ± 15.8 ml/min from 85.3 ± 31.3 ml/min to 73.2 ± 26.7 ml/min. The mean HbA1c decreased by 0.5 ± 1.6 % from 7.8 ± 2.1 % to 7.3 ± 1.8 %.
- c) 9 patients had baseline macroalbuminuria. Of these, none normalized, 4 became microalbuminuric (44.4%), 5 remained macroalbuminuric (55.5%). The mean UACR

fell by 453 ± 2085 mg/g from 1248 ± 2075 mg/g to 795 ± 1111 mg/g, a decrease of $11 \pm 98\%$. The mean creatinine increased from 1.15 ± 0.5 mg/dl to 1.6 ± 0.59 mg/dl. The mean eGFR decreased by 30.3 ± 23.3 ml/min from 88.5 ± 47.9 ml/min to 58.2 ± 37.5 ml/min. The mean HbA1c decreased by $1.5 \pm 3.3\%$ from $9.2 \pm 2.9\%$ to $7.7 \pm 1.5\%$.

Figure 1 below compares the evolution of albuminuria per annum between groups A and B.

2- Effect of exenatide on Nrf-2/keap-1 system, expression of anti-oxidant enzymes and TGF β -1 in MNC. Twenty four obese type 2 diabetics taking insulin were randomized to receive either exenatide 10 μ g twice daily or placebo twice daily for 12 weeks. Fasting blood samples were obtained at baseline and 3, 6 and 12 weeks later. Exenatide treatment suppressed Keap-1 protein by $21 \pm 8\%$ and increased the mRNA expression of NQO-1, GST-1P and HO-1 by $51 \pm 15\%$, $42 \pm 10\%$ and $39 \pm 10\%$, with an increase in NQO-1 protein by $25 \pm 10\%$ ($p < 0.05$) in MNC. Exenatide also suppressed plasma TGF β 1 concentrations by $20 \pm 7\%$ and SMAD-3 expression in MNC by $28 \pm 8\%$ (Figure 2, $p < 0.05$).

[figure not shown]

Figure 2: Change in mRNA expression of Keap-1, activity of Nrf-2, expression of NQO-1 and SMAD-3 in MNC and plasma concentrations of TGF- β 1 following placebo and exenatide 10 μ g daily for 12 weeks in type 2 diabetic subjects. N=12 each, data are presented as mean \pm SE. (*: $P<0.05$ by RMANOVA (compared to baseline), #: $P<0.05$ by Two-way RMANOVA compared to control groups.

3.2 Include complete citations or references.

Response:

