17.0 Data Management and Analysis

17.1 Describe the data analysis plan, including any statistical procedures. This section applies to both quantitative and qualitative analysis.

Response: **DATA ANALYSIS**

This is a prospective study to evaluate effect of Exenatide extended release treatment for 1 year on albuminuria levels in T2DM patients with micro- and macroalbuminuria compared to placebo. The similarities in baseline values between the study groups will be compared using appropriate parametric tests. Transformations of the data on order to meet statistical assumptions may be considered. All statistical analysis will be carried out using SPSS software (SPSS Inc, Chicago, Illinois) based on intention to treat principle. Data will be presented as mean±standard error. The primary endpoint of the study is the change from baseline in albuminuria level at weeks 12, 26, 39 and 56 following Exenatide extended release and placebo treatments. Fasting samples collected at weeks 0, 12, 26, 39 and 56 will be used for this assessment with values at week 0 considered as baseline. Changes from baselines from both drugs arms will be compared to those from the placebo arms in both the micro and macroalbuminuria groups. The statistical analysis will be done using mixed model for repeated measurement (MMRM) analysis with assigned α value of 0.05. Our preliminary data on retrospective analysis of the difference in albuminuria following GLP-1RA treatment for 2.5 yrs in T2DM patients with micro and macroalbuminuria show regression of albuminuria (UACR) by approximately 55mg/mg and 500mg/g (about 50% reduction), respectively.

The secondary end points include the comparison of the changes in albuminuria based on baseline albuminuria category (micro or macro), creatinine clearance, Cystatin C, TGF β , type I and IV collagen, CTGF, and fibronectin levels, the expression of SMAD3, SMAD4, NQO-1, GST-1P and HO-1, Nrf-2/keap-1 system activation between the Exenatide extended release and placebo groups and across albuminuria categories

17.2 If applicable, provide a power analysis.

NOTE: This may not apply to certain types of studies, including chart/records reviews, survey studies, or observational studies. This question is asked to elicit whether the investigator has an adequate sample size to achieve the study objectives and justify a conclusion.

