Response: Conservatively estimating a difference in the change from baseline in albuminuria after 1 year between the Exenatide extended release and placebo groups (across both albuminuria groups) of 60mg/g, with standard deviation of no more than 91mg/g, a sample size of 38 patients per group should provide adequate power ($\beta = 0.2$) to detect a significant difference ($\alpha = 0.05$). Assuming a drop-out rate of 15% and 2:1 drug: placebo randomization ratio, 60 active and 30 control will be recruited for a total of 90 patients (rounded up). Patients will be enrolled based on a predetermined stratification according to the two albuminuria categories (micro and macro at 1:1 ratio) with 45 patients in each.

17.3 Describe any procedures that will be used for quality control of collected data.

Response: Three investigators and research nurse will double check the accuracy of collected data. All laboratory testing will be standardized using references and standards.

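### At 2:1 allocation the MMRM should not rely on a variance shared by both arms: if placebo changes are more scattered, as the preliminary microalbuminuria data suggest, a nominal 95% interval for that stratum covers about 85%.

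*Combined protocol and SAP*

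**What the plan says.** Section 17.1, repeating section 2.1, gives the primary method in one sentence: "The statistical analysis will be done using mixed model for repeated measurement (MMRM) analysis", with alpha set at 0.05. It names SPSS and intention to treat. It gives no covariance structure, does not say whether the covariance is common to the arms, and names no degrees-of-freedom method or robust standard error. The endpoint is change from baseline in mg/g. Transformation is left as something that may be considered, with no rule. Arms are to be compared in both albuminuria groups, and the comparison by category is also listed as a secondary endpoint.

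Section 17.2 sets the allocation: "2:1 drug: placebo randomization ratio, 60 active and 30 control will be recruited". Section 4.1 divides this into 30 v 15 in each albuminuria stratum. Section 17.2 plans on a single spread for both arms: "of 60mg/g, with standard deviation of no more than 91mg/g, a sample size of 38 patients per group".

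The only arm-specific spreads are in the retrospective data of section 3.1. For microalbuminuria, users: "The mean UACR fell by 57.7 ± 64.5 mg/g"; non-users: "The mean UACR increased by 60 ± 201 mg/g". For the whole cohort the SDs of change are 193 mg/g in users and 454 in non-users ("in group B, UACR increased by 6 ± 454 mg/g").

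**The concern.** An MMRM with one covariance matrix for both arms compares means, but its standard error assumes that changes are equally spread in the two arms. At 1:1 a violation nearly cancels. At 2:1 it does not: the shared variance is estimated mainly from the larger arm, while the variance of the difference is driven mainly by the smaller one. If placebo patients vary more, the standard error is too small, intervals are too narrow and p-values are too low.

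Unequal spread is plausible if the drug works as hypothesised. In the microalbuminuria data, 6 of 36 non-users progressed to macroalbuminuria against none of 76 users. A treatment that prevents such excursions narrows the spread as well as moving the mean. The coverage error is the same whatever the true mean difference, so it would also affect the reported effect size of a drug that works.

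**Working it through.** **Plan's own figure.** With a difference of 60, a common SD of 91, two-sided alpha 0.05 (sidedness is not stated; two-sided assumed) and 80% power, the t-test solution is 37.09, so 38 per group. Then 76/0.85 = 89.4, so 90 patients. The plan's figure reproduces. With a common SD of 91, the shared-variance test at 60 v 30 rejects 5.0%.

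**Microalbuminuria contrast, 30 v 15, SDs 64.5 and 201 (section 3.1).** With complete data, a visit contrast from an unstructured MMRM with shared covariance equals a pooled-variance comparison of arm means at that visit.

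- Pooled variance: (29 × 64.5² + 14 × 201²)/43 = (120,647 + 565,614)/43 = 15,960.
- Squared SE the model would report: 15,960 × (1/30 + 1/15) = 1,596.
- True squared SE: 64.5²/30 + 201²/15 = 138.7 + 2,693.4 = 2,832.
- The SE is understated by √(2,832/1,596) = 1.33.
- P(|Z| > 1.96/1.33) is about 14%.

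Simulation with normal changes gives 14.5–14.7% rejection at equal means and about 85% coverage, both with no difference and with a true 60 mg/g difference. Separate arm variances (Welch) give about 5% and 95%. With 26 v 13 after 15% drop-out, shared-variance rejection is 14.9%. With the same SDs at 1:1 (45 v 45) it is 5.2%, so the allocation is the cause.

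**Range over the assumed SD ratio (placebo/exenatide), 60 v 30, shared variance**

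| Ratio | Rejection at equal means |
|---|---|
| 1.0 | 5.0% |
| 1.2 | 6.5% |
| 1.5 | 8.5% |
| 2.0 | 11% |
| 3.1 | 14% |

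**Are the preliminary ratios just baseline differences?** Randomisation should remove a baseline imbalance, so each ratio is set against the baseline SDs in section 3.1.

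| Group | Baseline SD, users v non-users | Follow-up SD | SD of change |
|---|---|---|---|
| Micro (76 v 36) | 68.8 v 48 | 48.7 v 199 | 64.5 v 201 (ratio 3.1) |
| Macro (15 v 9) | 579 v 2075 | 398 v 1111 | 606 v 2085 (ratio 3.4) |
| Whole cohort (275 v 191) | 250 v 500 | 147 v 302 | 193 v 454 (ratio 2.4) |

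In microalbuminuria the users started more spread out and ended less so, so baseline does not explain the ratio. In macroalbuminuria, SD of change over baseline SD is 606/579 = 1.05 against 2085/2075 = 1.00, so the ratio follows baseline. In the whole cohort it is 193/250 = 0.77 against 454/500 = 0.91, leaving about 1.18.

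**Pooled test, 30 v 15 per stratum, stratum term, shared variance.** Macroalbuminuria variance dominates here. With the preliminary SDs throughout, rejection is about 15%. With the micro SDs kept at 64.5 and 201 but equal macro SDs, it is 5.3% (SD 606) or about 5.0% (SD 2085). At a macro ratio of 1.2 it is 6.7%.

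**Cost of the remedy.** With equal SDs of 91 at 60 v 30, power for 60 mg/g is about 83.0% with a shared variance and 82.5% with arm-specific variances.

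**The case against.** Several objections stand. The plan never states a shared covariance, so the defect is an unspecified variance model, not a wrong one written down. The trial's planning assumption is a common SD. The unequal SDs come from unrandomised patients followed for a mean of 2.3 years (all users) and 3.6 years (all non-users), against one year here, and only 36 non-users had microalbuminuria.

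A reader might infer that the primary test has a 12–15% false-positive rate. The documents do not support that. The macro and whole-cohort ratios largely reflect baseline imbalance, and without them the pooled test stays near 5%. A drug with no effect at all leaves randomised arms equally spread, so the level holds. Inflation of the test needs a treatment that alters the spread but not the mean. Nor does the model test equal spread; that is only an assumption behind its standard error.

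A log transformation might also remove the problem. The one log-scale result in section 3.1 (0.49 v 0.056) is not labelled SD or SE. Read as SDs, it gives 0.7% rejection, the opposite direction; one reading as SEs, taking 0.49 to mean 0.049, gives about 4.6%. It cannot settle the matter, and the plan does not commit to logs. On the percent-change scale, non-users are again more variable (74 v 311 micro, 57 v 98 macro).

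Finally, a full four-visit covariance has 10 parameters in each arm-by-stratum cell, with about 13 placebo completers per stratum. That is a fair criticism of a remedy resting on arm-specific matrices alone.

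**Conclusion.** The concern holds as a gap in specification with a real possible consequence. If the microalbuminuria spreads recur on the mg/g scale and the model shares its covariance, the interval for that contrast covers about 85% instead of 95%, and the test rejects about 15% at equal mean changes. These are sensitivity figures. They assume normal changes, complete data, a single visit contrast and the retrospective SD ratio of 3.1; smaller ratios give the smaller errors tabulated above. For the pooled primary test, material inflation is possible but not established. The point is worth acting on because protection is nearly free, not because the trial is shown to be invalid.

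**What to change.** In sections 2.1 and 17.1, state that treatment contrasts, pooled and by albuminuria category, will not rely on a variance shared across arms. Use either an arm-specific residual covariance with Satterthwaite or Kenward-Roger degrees of freedom, or a robust (sandwich) covariance with a small-sample correction. Make the robust version the default or the stated fallback, because a full matrix by arm and stratum may be unstable with 13–15 placebo patients per stratum. Confirm that the named software can fit the chosen option. Keep the rule on whichever scale is analysed.

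This takes one or two sentences and no new patients or data. The cost is about 0.5 points of power and slightly wider intervals if the spreads prove equal, and possible use of the fallback if the model does not converge.

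### The SD of at most 91 mg/g behind the sample size is not supported by the protocol's own UACR data: raw-scale power at 60 mg/g is about 9% (about 26% with a very favourable time-scaling of the SD), not 80%

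*Combined protocol and SAP*

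**What the plan says.** Section 17.2, with the same text in 2.1, assumes a difference in 1-year albuminuria change "across both albuminuria groups) of 60mg/g, with standard deviation of no more than 91mg/g". From this it derives 38 patients per group for 80% power at α = 0.05. Allowing for 15% drop-out and 2:1 allocation, it recruits 60 active and 30 placebo patients, 45 in each albuminuria stratum. It cites no source for the 91.

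The only UACR-change SDs in the protocol are in the preliminary data of section 3.1:

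- GLP-1RA users, micro (n = 76): "The mean UACR fell by 57.7 ± 64.5 mg/g from 103.5 ± 68.8 mg/g to 45.8 ± 48.7 mg/g"
- GLP-1RA users, macro (n = 15): "The mean UACR fell by 500 ± 606 mg/g from 936 ± 579 mg/g to 436 ± 398 mg/g"
- Non-users, micro (n = 36): "The mean UACR increased by 60 ± 201 mg/g from 85 ± 48 mg/g"
- Non-users, macro (n = 9): UACR "fell by 453 ± 2085 mg/g from 1248 ± 2075 mg/g to 795 ± 1111 mg/g"

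On the analysis, section 17.1 says: "The statistical analysis will be done using mixed model for repeated measurement (MMRM) analysis". It names no covariates. On scale it says only: "Transformations of the data on order to meet statistical assumptions may be considered".

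**The concern.** The 91 mg/g is put forward as an upper bound for a sample that is half macroalbuminuric, yet only the microalbuminuric users have a reported SD below it. The whole user group, of whom only 15 of 275 were macroalbuminuric, already has a change SD of 193 mg/g.

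A common 60 mg/g also means different things in the two strata. It is 58% of the users' micro baseline (60/103.5) and 6% of their macro baseline (60/936). A pooled raw mean therefore mostly reflects the macro half, and a few patients with very high UACR can drive it.

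Two things are at stake. The trial would probably miss the effect it was sized for, and a non-significant result could be misread as no effect. And with scale and covariates undecided, the primary p-value can depend on a choice made after the data are seen.

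**Working it through.** **Inputs.** Difference 60, SD 91, α 0.05 (two-sided assumed; the plan does not say), 15% drop-out, 60:30 recruited, 1:1 micro:macro (section 17.2). Completers: 60 × 0.85 = 51 and 30 × 0.85 = 25.5. SDs and mean follow-up (2.3 years for users, 3.6 for non-users) are from section 3.1. Power is from the two-sample noncentral t unless stated.

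**The plan's own figure.** At 60/91, 38 per group gives 81.0% power (37 gives 79.9%), and 76/0.85 = 89.4, rounded up to 90. The arithmetic reproduces. The 2:1 split with 51:25.5 completers gives 76.5%, so power is about 77% even at SD 91.

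**SD for a 1:1 mix** (within stratum), √((SD_micro² + SD_macro²)/2):

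- Users: √((64.5² + 606²)/2) = 431
- Non-users: √((201² + 2085²)/2) = 1481

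**What 91 would require.** With micro at 64.5, the macro SD must be √(2 × 91² − 64.5²) = 111. The 95% interval for the users' 606 (14 df, normal theory) is 444 to 956, which gives mixed SDs of 317 to 677. (64.5 × √2 = 91.2, so 91 may derive from the micro stratum alone. That is an inference; the plan does not say so.)

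**Baseline adjustment.** The printed SDs imply r = (s_b² + s_f² − s_c²)/(2 s_b s_f), where b, f and c are baseline, follow-up and change. This is 0.44 in micro and 0.27 in macro users. Residual SDs s_f√(1 − r²) are 43.7 and 383, and their 1:1 mix is 272.

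**Power at 60 mg/g, 51:25.5:**

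| SD (mg/g) | Basis | Power |
|---|---|---|
| 91 | as stated | 77% |
| 431 | users' SDs in both arms | 9% |
| 317 to 677 | 95% interval of macro SD | 12% to 6.5% |
| 431 and 1481 | each group's own SDs (normal approximation) | 5.5% |
| 193 | whole user group, mostly normoalbuminuric | 24% |
| 272 | users, baseline-adjusted | 15% |
| 187 | 431/2.3, SD shrinking in full proportion to time | 26% |
| 118 | 272/2.3, both concessions | 54% |

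One more concession gets below 91. The lower 95% limit of the macro residual SD is 277 (13 df); mixed with 43.7 it gives about 199, and 199/2.3 is about 86. That stacks three favourable assumptions and uses the users' SDs for placebo too.

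**Other true differences.** The user-minus-non-user contrast averaged over strata is ((57.7 + 60) + (500 − 453))/2 = 82 mg/g; power at SD 431 is 12%. The average of the falls of 55 and 500 quoted in section 17.1, with no placebo change, is about 278 mg/g; power is 75%. The standardised difference detectable with 80% power is 0.688, which is 297 mg/g at SD 431 and 129 mg/g at SD 187.

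**Log scale.** The detectable reduction is 1 − exp(−0.688 s), with s the SD of ln-change. For assumed s of 0.6, 0.8 and 1.0 it is 34%, 42% and 50%. Section 3.1 prints "HbA1c adjusted log change in UACR in group A was -0.09 ± 0.49 and in group B was 0.08 ± 0.056". The log base is not given and the two spreads differ about nine-fold (0.49/0.056 = 8.75). Read as an SD, 0.49 gives 29% (natural log) or 54% (log10: 0.49 × ln 10 = 1.128). These figures cannot settle the SD, all the more because 183 of the 275 users were normoalbuminuric at baseline.

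**The case against.** The strongest reply is that other analyses come close to nominal power. Weighting the strata by inverse variance, with 60 mg/g true in each and the users' SDs in both arms, gives about 78%. Enrolment is stratified, and section 17.1 speaks of comparing changes within both albuminuria groups. But the plan does not specify this weighting. The micro stratum would carry 99% of the weight (606²/(606² + 64.5²)), so the result is nearly a micro-only estimate. With each group's own SDs the figure falls to 18%.

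Second, the calculation above uses one timepoint, while the MMRM has four post-baseline visits. If the effect were averaged over visits with a between-visit correlation of 0.5 to 0.9 (an assumption), the 26% case becomes 27 to 38% and the 54% case 58 to 74%. The 9% case hardly moves (9 to 11%).

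Third, the 606 comes from 15 retrospective patients followed for longer, under different entry conditions, and the interval of 444 to 956 assumes normality for a visibly skewed measure. This stands: 9% is a central reading, not a precise one, and 26% is not a strict ceiling.

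Fourth, a transformation is permitted, and the investigators used logs in their own retrospective work. For a 50% reduction, ln-change SDs of 0.6 to 1.0 give over 99% down to 81% power, so the design may be adequate on that scale. This also stands, but it argues for committing to the log scale. It does not support a mg/g calculation or a choice left open.

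**Conclusion.** The concern holds. The sample-size arithmetic is right for its inputs, but the SD is not supported by anything in the protocol. With the protocol's own SDs, raw-scale power at 60 mg/g is about 9%. It is about 26% under a very favourable time-scaling and 54% with full baseline adjustment on top. Nominal power returns only with stacked favourable assumptions or an analysis the plan does not name.

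The figures assume a two-sided 5% test, 51:25.5 completers, a true difference of exactly 60 mg/g and, except in the 5.5% case, the users' SDs in both arms, which favours the plan. A much larger true raw difference would raise power, but the claim in 17.2 is made at 60. The open scale and the missing covariates are faults whatever the exact SD. This must be corrected, because it concerns the primary endpoint and the sole justification for 90 patients.

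**What to change.** - **Sections 2.1 and 17.1:** replace the optional transformation with a prespecified primary MMRM on change in ln(UACR). Include treatment, visit, treatment-by-visit, baseline ln(UACR) and the albuminuria randomisation stratum. Report the ratio of geometric means with its 95% CI, and keep the mg/g change as supportive.
- **Section 17.2, and its copy in 2.1:** withdraw the claim of 80% power at 60/91 mg/g. State the percentage reduction detectable with about 51:26 completers, taking the SD of ln-change by stratum from the investigators' retrospective cohort (112 micro, 24 macro). Until that is done, label the SD an assumption and show the range: 0.6 to 0.8 gives about 34 to 42%, and 1.0 about 50%.

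The cost is one protocol amendment, made before unblinding, with no extra patients, visits or tests. The primary effect becomes relative instead of absolute, and the power statement will be less favourable than the present one.

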4.0 Study Design

4.1 Describe and explain the study design (e.g. case-control, cross-sectional, ethnographic, experimental, interventional, longitudinal, observational).

Response:

This is a single center, prospective, double blind, randomized, placebo –controlled in a parallel design study. The study will be conducted at the Diabetes – Endocrinology Center of Western New York under the direction of [name], M.D, [name], MD and [name], PhD.

Ninety (90) T2DM patients with micro- or macroalbuminuria (45 each) will be enrolled and randomized into 2 groups to receive placebo or exenatide-extended release treatments for 1 year. The study groups and treatment arms of this study are:

1. T2DM with Microalbuminuria: 30 patients on Exenatide extended release and 15 patients on placebo for 1 year
2. T2DM with Macroalbuminuria: 30 patients on Exenatide extended release and 15 patients on placebo for 1 year

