20.0 Withdrawal of Subjects

N/A: This study is not enrolling subjects. This section does not apply.

20.1 Describe anticipated circumstances under which subjects may be withdrawn from the research without their consent.

Response: The principal investigator of the study can remove a participant from the research study without their approval if for any reason he/she feels is appropriate, including

- i. Pregnancy
- ii. Developing conditions included in the exclusion criteria
- iii. Subjects decision to withdraw from the study
- iv. Severe side effects specific to study drugs
- v. Any medical condition that may place patient at risk of further complications
- vi. failure to take the medication as instructed, failure to keep your scheduled appointments,
- vii. cancellation of the study by the sponsor, or other administrative reasons.

20.2 Describe any procedures for orderly termination.

NOTE: Examples may include return of study drug, exit interview with clinician. Include whether additional follow up is recommended for safety reasons for physical or emotional health.

Response: If a subject withdraws from the research, the data collected to that point will be used toward the research finding. If applicable the subject will have to bring back any unused research drug and or device. If necessary, they will be asked to complete an end of study visit for their safety.

20.3 Describe procedures that will be followed when subjects withdraw from the research, including retention of already collected data, and partial withdrawal from procedures with continued data collection, as applicable.

Response: If a subject withdraws from the research, the data collected to that point will be used toward the research finding. If applicable the subject will have to bring back any unused research drug and or device. If necessary, they will be asked to complete an end of study visit for their safety.

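### The stated 80% power belongs to 38 v 38 completers; splitting the same 90 patients 60:30 gives about 76–78% once drop-outs are counted as lost

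*Combined protocol and SAP*

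**What the plan says.** Section 17.2, repeated in 2.1, takes a difference in change from baseline between the arms ("across both albuminuria groups) of 60mg/g"), "with standard deviation of no more than 91mg/g" and alpha 0.05. From these it concludes that "a sample size of 38 patients per group should provide adequate power", with the type II error given as 0.2. It then brings in 15% drop-out and 2:1 randomisation together and states that "60 active and 30 control will be recruited for a total of 90 patients (rounded up". Section 4.1 confirms the split in each albuminuria stratum: "30 patients on Exenatide extended release and 15 patients on placebo for 1 year".

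No calculation for unequal groups is shown, and no power is given for 60:30.

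Two other statements bear on the point. Section 17.1 says: "The statistical analysis will be done using mixed model for repeated measurement (MMRM) analysis". Sections 20.2 and 20.3 say that when a subject withdraws, "the data collected to that point will be used toward the research finding".

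**The concern.** The per-group number describes neither arm of this trial. Only 30 patients are randomised to placebo, so that arm cannot reach 38 even before drop-out. The total, on the other hand, is exactly what two equal groups of 38 need after a 15% allowance. It looks as if the total was worked out for equal groups and then divided 2:1.

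For a fixed total, a 2:1 split estimates the treatment difference less precisely than a 1:1 split, so the power attached to 38 per group does not carry over. At stake is the accuracy of the stated type II error, on which anyone interpreting a null result would rely.

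**Working it through.** **Inputs (section 17.2).** Difference 60 mg/g; SD 91 mg/g; alpha 0.05; target power 80%; drop-out 15%; 60 active and 30 placebo randomised. Sidedness is not stated. Two-sided is assumed, because a one-sided test would need only 29 per group and so cannot be the source of 38.

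**Formula.** For group sizes n1 and n2, the noncentrality is δ = (60/91) / √(1/n1 + 1/n2). Power comes from the noncentral t distribution with n1 + n2 − 2 degrees of freedom or, as an approximation, from Φ(δ − 1.96).

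**Step 1: reproduce the 38.** With equal groups:

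| Completers | δ | Power (t) | Power (normal) |
|---|---|---|---|
| 37 v 37 | 2.84 | 79.9% | 80.9% |
| 38 v 38 | 2.87 | 81.0% | 82.0% |

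So 38 is the smallest equal group size that reaches 80% by the t-test.

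**Step 2: reproduce the 90.** 2 × 38 = 76, and 76 / 0.85 = 89.4, rounded up to 90. The match is exact. The document does not say how 90 was reached, so its 1:1 origin is an inference. A calculation made for 2:1 would give a different total (step 5).

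**Step 3: apply the plan's split and drop-out.** 60 × 0.85 = 51 and 30 × 0.85 = 25.5. The equal-allocation equivalent is 2 / (1/51 + 1/25.5) = 34.0 per group. This is 8/9 of the 38.25 per group that the same 76.5 completers would give at 1:1.

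**Step 4: power at that split.** δ = (60/91) / √(1/51 + 1/25.5) = 2.72.

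| Completers | Power (t) | Power (normal) |
|---|---|---|
| 51 v 25 | 76.0% | 77.1% |
| 51 v 25.5 | 76.5% | 77.6% |
| 51 v 26 | 77.1% | 78.1% |

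Every variant is below 80%.

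**Step 5: what 80% would take.** At 51 v 25.5 completers, 80% power is reached at a difference of 62.6 mg/g (t) or 61.8 mg/g (normal). To hold 60 mg/g at exactly 2:1, 54 v 27 falls just short (78.9% t, 79.9% normal), while 56 v 28 suffices (80.4% t, 81.3% normal). That is 84 completers, and 84 / 0.85 = 98.8, so about 99 randomised.

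**Step 6: allow for partial data.** The documents do not say how much information a drop-out contributes to the mixed model. Assume a fraction f of a completer's information, so the effective sizes are 51 + 9f and 25.5 + 4.5f:

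| f | Power (t) |
|---|---|
| 0 | 76.5% |
| 0.25 | 78.3% |
| 0.50 | 80.0% |
| 1 | 83.1% |

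The break-even fraction is about 0.50 by the t-test and about 0.35 by the normal approximation.

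**The case against.** The arithmetic is not in dispute. The case against is that 76–78% is a worst-case figure and that the point is small.

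- **Drop-outs.** The planned mixed model and the retention of data up to withdrawal mean that drop-outs are not wholly lost. The range in step 6 runs from 76.5% to 83.1% and straddles 80%. This stands as a qualification: under the planned analysis a shortfall is possible rather than proven. But the plan's own power statement takes no such credit. It inflates for drop-out as complete loss, and on that convention its figure is not met.
- **SD as an upper bound.** The plan gives 91 as a maximum. At 51 v 25.5 completers, 80% is reached at an SD of 87.2 (t) or 88.3 (normal), only 3–4% lower. That is true, but the plan attaches the type II error of 0.2 to 91, and that is the claim being checked.
- **Is 91 realistic at all?** The retrospective data in section 3.1 show SDs of change of 64.5 mg/g in microalbuminuric and 606 mg/g in macroalbuminuric GLP-1RA users, and half of this trial is to be macroalbuminuric. Beside that question a correction of 2–4 points is minor, and a restated power figure could lend the SD authority it has not earned. This is a fair warning and a separate issue. It does not rescue the stated figure, and it is why any restated power must be expressly conditional on an SD of 91.
- **Origin of the 90.** That it was carried over from 1:1 is inferred. The conclusion does not depend on it: 51 v 25.5 completers fall below 80% however the total was reached.

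**Conclusion.** The concern holds. On the plan's own inputs, the type II error for the design as allocated is about 0.23 (range 0.22 to 0.24 across methods and rounding), not 0.20.

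This rests on two-sided alpha 0.05, a difference of 60 mg/g, an SD of 91 mg/g and 15% drop-outs contributing nothing. It takes the difference and SD as given and does not judge whether they are realistic.

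The error is clear but modest, at 2 to 4 percentage points of power. Nothing is wrong with randomising 2:1; only the power statement attached to it is wrong. It should be corrected, but it does not threaten the validity of the trial.

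**What to change.** In sections 2.1 and 17.2, replace the sentence on 38 per group and its type II error with wording to this effect:

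> 60 patients will be randomised to exenatide extended release and 30 to placebo. After 15% drop-out about 51 and 25.5 completers are expected. If the SD is 91 mg/g, this gives about 76–78% power (two-sided alpha 0.05) for a difference of 60 mg/g, and 80% power for about 63 mg/g. Any gain from partial data in the mixed model is not counted.

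Keep the 2:1 ratio and the total of 90. The cost is one statement reworded in two places and a slightly less favourable power figure. Sample size, allocation, visits and analysis do not change. If the sponsor prefers to keep 80% power at 60 mg/g with drop-outs counted as lost, the alternative is to randomise about 99 (66:33), nine more than planned.
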